#### **Efficacy Analysis**

The primary analysis will be conducted on the population of subjects who complete all study visits. A secondary analysis will be conducted on the intent to treat population; that is, at each time point, all subjects who completed both the baseline evaluation and that evaluation will be included in the analysis. Additional subsets of the subject

population may be analyzed for informational purposes only. Other than the subject inclusion criterion, all analyses will be conducted identically as follows:

For each examination and each index, subjectwise mean Index scores will be obtained by calculating the average of the index scores evaluated at all individual measurement sites within the mouth. In addition to these 'whole-mouth' scores, subjectwise scores will also be obtained by calculating the average index scores over selected subsets of sites within the mouth. These subsets will include: Proximal sites; Marginal sites (MGI and GBI only); Gingival sites (PI only); Facial sites; Lingual sites; Posterior sites; Anterior Facial sites; and Anterior Lingual sites.

All statistical analyses will be based on the subjectwise Index scores. Separate analyses will be performed based on the subjectwise whole-mouth scores, as well as the subjectwise scores obtained from each of the selected subsets of the mouth.

The primary endpoints employed for the treatment comparisons in this study will be the month 6 Index scores. Additional analyses will be conducted on the Index scores collected at other time points. The comparison of the study treatments will employ an analysis of covariance (ANCOVA) model, with the associated baseline Index score included as a covariable. The ANCOVA model will include the factors: subject, treatment, and baseline Index score. Post-ANCOVA pairwise treatment comparisons of the adjusted means will be performed using t-tests utilizing Tukey's adjustment for multiple comparisons. Within-treatment comparisons of the mean baseline Index scores to the mean month 6 (or other post-baseline time point) Index scores will be performed using paired t-tests.

The comparison of the study treatments at baseline for each index will be performed using the same model described above, without the inclusion of the covariable.

All statistical tests of hypotheses will be two-sided, and employ a level of significance of  $\alpha = 0.05$ .

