#### VI. STUDY DESIGN

This parallel group, double-blind, randomized, single center, IRB/IEC-approved study will enroll approximately 320 subjects to ensure that approximately 100 subjects per group (300 subjects total) will complete the 6-month study. The Study Examiner will screen for subjects that meet the enrollment criteria. Subject group stratification will be based on smoking and tobacco use. Subjects will be randomly assigned to one of three dentifrice treatment groups. Oral soft and hard tissue examinations, gingivitis, bleeding and plaque assessments will be done at baseline and after 6 weeks and 3- and 6-months. Following an initial supervised tooth brushing, subjects will brush unsupervised with their assigned toothpaste at home for the 6-month treatment phase of the study, 2 times daily for 1 minute per brushing. Subjects will be provided with a timer and will maintain a daily diary of their brushing and record any oral effects they experience. Compliance will be assessed by subject diary and weight-loss of returned test products at each visit. The examiner will be blinded to the product codes/identification and product assignments.

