#### VIII. TEST PRODUCTS AND CLINICAL SUPPLIES

## **Test Products** Two baking soda-containing dentifrices:

containing 20% baking soda ( 1. dentifrice with 35% baking soda minus amorphous calcium phosphate (ACP) **Negative Control** 

with 0% baking soda

Clinical Supplies The sponsor will provide the following items to the study site:

- 3916-23A Toothpaste
- 3916-23B Toothpaste
- 3916-23C Toothpaste

\*\* The 18-week visit will include only: Diary review, product weights, product distribution, sensory evaluation, adverse events, update of inclusion/exclusion and any medical changes.

Toothbrushes -2 per subject to be dispensed at the baseline and 3 month visits.

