#### 18-Week Compliance Visit (±7 Days)

At Week 18, subjects will report to the study site with their dentifrice, toothbrush, diary and timer for a compliance visit. Products will be weighed and diaries will be reviewed. Subjects will provide a sensory evaluation as described at the 6-week visit. The subjects will be provided with one additional tube of toothpaste.

The subject will be questioned about dentifrice use compliance by asking "Your brushing schedule is twice daily (morning and evening), for 1 minute per brushing, using only the toothpaste and toothbrush provided by All Sum Research. Have you deviated from that schedule at all?" (e.g. made any changes or forgotten to use the toothpaste). A "yes" or "no" answer to the question must be obtained. For all "yes" answers, the study site staff must determine what changed. Subjects will be assessed for any AEs they may have experienced since the previous visit and any changes to inclusion/exclusion criteria or medical updates.

The subjects will be reminded not to use any other oral hygiene products for the duration of the study. Subjects will be scheduled for their next visit and will be instructed to refrain from any oral hygiene procedures the morning of their next visit and to refrain from eating, drinking and smoking for approximately 4 hours prior to their visit. They will be advised to follow the instructions carefully and return to the study site with their assigned toothpaste, toothbrush, timer and diary at their next appointment. The study personnel will reinforce the product use instructions and study instructions and will schedule subjects for the 6-month visit. Subjects will receive a reminder call prior to their next visit.

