#### XI. STUDY ASSESSMENTS

A qualified examiner will evaluate the oral soft and hard tissues, gingival index (MGI), bleeding index (GBI) and plaque index (PI) (Soparkar Modified Turesky) for all subjects at all visits except the 18-week compliance visit. The examiner will be blinded to the treatment randomization assignments.

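### The primary efficacy set requires attendance at every visit, although the month-6 endpoint needs only the baseline and month-6 exams

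*Combined protocol and SAP*

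**What the plan says.** Section XIV, Efficacy Analysis, defines two analysis sets. For the first: "The primary analysis will be conducted on the population of subjects who complete all study visits". The second, which the plan labels intent to treat, is secondary and is built exam by exam: "at each time point, all subjects who completed both the baseline evaluation and that evaluation will be included in the analysis". Apart from who is included, the two analyses are to be run identically.

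The same section fixes the endpoint: "The primary endpoints employed for the treatment comparisons in this study will be the month 6 Index scores". Treatments are compared by ANCOVA with the baseline score of the same index as covariable. No week-6 or month-3 score enters the month-6 comparison; other time points get additional analyses of their own.

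The visits between baseline and month 6 are week 6, month 3 and week 18. The last differs in kind. Section X describes it so: "At Week 18, subjects will report to the study site with their dentifrice, toothbrush, diary and timer for a compliance visit". The Study Schedule footnote (printed under section VIII) limits its content: "The 18-week visit will include only: Diary review, product weights, product distribution, sensory evaluation, adverse events", plus updates of eligibility and medical changes. Section XI schedules the tissue exam and the three indices "for all subjects at all visits except the 18-week compliance visit". Nothing exempts this visit from the all-visits requirement.

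**The concern.** Whether a subject attends an interim visit is decided after randomisation. It may depend on tolerability, perceived benefit or general reliability, and these may differ between products. Removing subjects on that basis can disturb the balance that randomisation created. Sometimes such exclusion is unavoidable because the outcome is missing. Here it is not: the subjects in question have both scores that the model uses.

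The 18-week visit is the clearest case. It yields no efficacy measurement, yet missing it removes a valid month-6 outcome from the primary comparison.

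The wider analysis would reveal a disagreement between the two sets, but the plan gives primary status to the more selected one.

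**Working it through.** **Reading the rule against the endpoint**

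1. Scores needed for the month-6 ANCOVA: baseline and month 6.
2. Attendance needed for the primary set: baseline, week 6, month 3, week 18 and month 6.
3. The difference is three interim visits. A subject with both scores who misses any of them is in the secondary month-6 analysis but not in the primary one.

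**The plan's own figures**

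- Enrolment (Sample Size): 320 enrolled for 300 completing. Implied loss = 20/320 = 6.25%, and 300/(1 - 0.0625) = 320. This is consistent.
- Power (Sample Size): over 95% for a 20% difference with 100 per group. Using Φ(20/(CV × √(2/100)) - 1.96), PI (CV 18.1%) and MGI (CV 7.2%) give about 100%. GBI (CV 61.3%) gives Φ(2.307 - 1.96) = 63.6%, so the statement does not reproduce for GBI. That is a separate matter, and the present point does not rest on it.

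**How many subjects could be affected (illustration)**

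The documents give no missed-visit rate. Assume a share p of month-6 attenders misses each of the three interim visits, with p from 0 to 3%.

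- Independent misses: share lost m = 1 - (1 - p)³.
- Fully clustered misses (the same subjects miss all three): m = p.
- Independent misses, lost for the 18-week visit alone: p(1 - p)².
- Relative interval width = 1/√(1 - m), assuming equal loss across groups and the same residual SD in both sets.

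| p | Independent: m | per 300 | width | Clustered: per 300 | width | 18-week only: share | per 300 |
|---|---|---|---|---|---|---|---|
| 0% | 0% | 0 | 1.000 | 0 | 1.000 | 0% | 0 |
| 1% | 2.97% | 8.9 | 1.015 | 3 | 1.005 | 0.98% | 2.9 |
| 2% | 5.88% | 17.6 | 1.031 | 6 | 1.010 | 1.92% | 5.8 |
| 3% | 8.73% | 26.2 | 1.047 | 9 | 1.015 | 2.82% | 8.5 |

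**Against the plan's loss allowance**

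- If 300 of 320 attend every visit, at most 20 subjects can differ between the sets, and only if nobody misses month 6. Width is then at most 1/√0.9375 = 1.033.
- If the 6.25% loss is spread equally and independently over the four post-baseline visits, (1 - p)⁴ = 0.9375 gives p of about 1.6%. Then 320 × 0.984 = 314.9 subjects attend month 6 and 300 attend every visit. About 15 move (4.7% of month-6 attenders), with width about 1.025.

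**Per-group size and power**

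Start from 320/3 = 106.7 per group, with an independent miss probability p at each of the four post-baseline visits. The all-visit set is 106.7(1 - p)⁴ and the month-6 set is 106.7(1 - p).

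| p | All-visit set | Baseline + month-6 set |
|---|---|---|
| 1% | 102.5 | 105.6 |
| 2% | 98.4 | 104.5 |
| 3% | 94.4 | 103.5 |
| 5% | 86.9 | 101.3 |

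The all-visit set falls below the planned 100 per group once p exceeds about 1.6%. The wider set stays above 100 throughout this range. Power for PI and MGI is about 100% in either set. For GBI (two-sided 0.05, no Tukey adjustment, no covariate gain) it is 64.6% against 65.9% at p = 1%, and 57.6% against 64.1% at p = 5%.

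No bias figure is given. It would need the outcome difference between attenders and non-attenders by group, and the documents supply nothing from which to set it.

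**The case against.** - **The affected subjects may not exist.** Subject Discontinuation (section XIII) treats non-adherence to the protocol as grounds for discontinuation, and Subject Completion defines completers more strictly still. If every missed visit led to discontinuation, these subjects would have no month-6 exam and the two sets would coincide. But no section says that one missed visit has this effect, and subjects with low product weights are to be retrained. The size of the group is uncertain. If it is empty, the swap does no harm.
- **The wider analysis is already planned.** True, so a disagreement would be visible and the fix is cheap. It does not justify giving the more selected set primary status.
- **The effect is small and no bias is shown.** This largely stands. The upper end of the assumed range (26 per 300) exceeds the plan's whole loss allowance, which would cap it at 20 subjects. The allowance is an expectation, though, not a limit. Blinding of the examiner, study personnel, subjects and assigning staff (sections VI, VII and VIII) limits bias, but cannot ensure that attendance is unrelated to product.
- **Attendance stands in for exposure.** A tube is handed out at each interim visit; for week 18, "The subjects will be provided with one additional tube of toothpaste". A missed visit may therefore interrupt supply. But the plan measures use separately: "Compliance will be assessed by subject diary and weight-loss of returned test products at each visit". Those checks take place at visits, so a missed visit delays or loses one of them. Even so, the rule keeps a poor user who attends and drops a faithful user who misses week 18.
- **The replacement set also depends on attendance.** Correct: attending month 6 is itself a post-randomisation event. The change reduces the selection without removing it.

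**Conclusion.** The concern holds. On the text, subjects with both scores needed for the primary endpoint are excluded from the primary analysis for missing visits that the endpoint does not use, one of which has no index scored. Confidence in that reading is high.

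The consequence is modest and partly unknown. The number affected runs from none to about 26 per 300 under the assumed 0-3% miss rate per visit, or at most 20 if losses stay within the plan's 6.25% allowance. The corresponding loss of precision is at most 4.7% or 3.3% in interval width. The main issue is avoidable selection after randomisation, whose size and direction cannot be determined from the documents. The change is worth making because it costs little, not because harm has been shown.

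**What to change.** In Efficacy Analysis, define the primary month-6 population as all randomised subjects with a baseline and a month-6 score, analysed by assigned group, whatever their attendance at week 6, month 3 or week 18. Keep all-visit completers as a sensitivity analysis.

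State plainly that subjects without a month-6 exam are in neither month-6 analysis. A repeated-measures model using the week-6 and month-3 scores could be added as an optional sensitivity analysis for them.

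Cost: wording only, made as a written amendment with the approvals that the Protocol Amendments section requires. Both analyses are already specified and otherwise identical, so no data, visits or subjects are added. The one downside is that the estimated effect may be slightly smaller, because subjects with interrupted supply or attendance are included.

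### The primary ANCOVA lists subject as a factor with only one score per subject; as a fixed factor it leaves no error degrees of freedom, so the term should be deleted

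*Combined protocol and SAP*

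**What the plan says.** Everything relevant is in section XIV, Efficacy Analysis, except the design statement in section VI.

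- **Model:** "The ANCOVA model will include the factors: subject, treatment, and baseline Index score". No other sentence gives the terms of the primary model.
- **Unit of analysis:** "For each examination and each index, subjectwise mean Index scores will be obtained by calculating the average of the index scores" over the sites in the mouth, and "All statistical analyses will be based on the subjectwise Index scores". Whole-mouth scores and each site subset are analysed separately.
- **Primary time point:** "The primary endpoints employed for the treatment comparisons in this study will be the month 6 Index scores". Other time points get additional analyses. No visit term, treatment-by-visit term or covariance structure is named.
- **Comparisons:** "Post-ANCOVA pairwise treatment comparisons of the adjusted means will be performed using t-tests", with Tukey's adjustment, two-sided at 0.05.
- **Baseline comparison:** it "will be performed using the same model described above, without the inclusion of the covariable".
- **Reach:** "Other than the subject inclusion criterion, all analyses will be conducted identically as follows".
- **Design (section VI):** parallel groups, and "Subjects will be randomly assigned to one of three dentifrice treatment groups".

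**The concern.** A subject term can be separated from residual error only when subjects contribute more than one row. Here each analysis has one row per subject, and both treatment and baseline score are constant within a subject. A fixed subject factor therefore fits every observation exactly. It absorbs treatment and baseline and leaves no residual from which to estimate error.

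The sentence at fault is the one that defines the primary model. Because all analyses are to be run identically apart from the analysis set, it also governs the intent-to-treat analysis, all three indices, the other post-baseline time points and every site subset. The within-treatment paired t-tests do not use this model and are unaffected.

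As it stands, the statistician must depart from the written primary model in order to produce any between-group result.

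**Working it through.** The plan states no degrees of freedom, so there is no figure of its own to reproduce. The df follow from the design.

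**Inputs.** N = 300 completers, 100 in each of 3 groups (section XIV, Sample Size; section VI). One row per subject and one continuous baseline covariate (section XIV, Efficacy Analysis). Two-sided alpha 0.05.

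**1. Subject as a fixed factor, month 6.** The model is Y_i = μ + s_i + τ_t(i) + β·x_i + e_i, where t(i) is the subject's treatment and x_i the baseline score.

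- The 300 subject indicator columns already span all 300 rows: rank[subject] = 300.
- Each treatment column is the sum of the indicators of its 100 subjects: rank[subject, treatment] = 300, so treatment adds 300 − 300 = 0 df.
- The baseline column is a weighted sum of the same indicators: rank[subject, treatment, baseline] = 300, so baseline adds 0 df.
- Residual df = N − rank = 300 − 300 = 0.

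The order of entry does not rescue it:

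| Order | Subject df | Treatment df | Baseline df | Error df |
|---|---|---|---|---|
| Subject first (as listed) | 299 | 0 | 0 | 0 |
| Treatment, baseline, then subject | 296 | 2 | 1 | 0 |

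Each row totals 299 = N − 1. A pairwise t statistic needs the error mean square, SSE / df_error, which here is 0/0.

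**2. Baseline comparison with the covariable removed.** rank[subject, treatment] = 300, so residual df = 300 − 300 = 0.

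**3. Subject deleted.**

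- Month 6: rank[intercept, treatment, baseline] = 1 + 2 + 1 = 4. Treatment df = 2 and residual df = 300 − 4 = 296. The Tukey critical |t| for three groups is q(0.95; 3, 296)/√2 = 2.356.
- Baseline: rank[intercept, treatment] = 3, so residual df = 300 − 3 = 297.
- Intent-to-treat, if all of the approximately 320 enrolled contributed: 320 − 4 = 316, and 320 − 3 = 317 at baseline. With subject retained, residual df are 0 in both.

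**4. Subject as a random effect.** With one row per subject the covariance matrix is (σ²_subject + σ²_error)·I. Only the sum of the two variances is identified, and generalised least squares equals ordinary least squares. In one simulated data set (illustrative, not trial data) with total variance 0.04, subject variance was set to 0, 0.02 and 0.03. All three settings gave treatment coefficients −0.06608 and −0.2112 and the same restricted log-likelihood, 328.997. The term changes nothing.

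**5. Three post-baseline visits stacked, subject fixed and a visit term added.** There are 3 × 300 = 900 rows. The rank is 300 (subject) + 2 (visit) = 302, so error df = 900 − 302 = 598. Treatment adjusted for subject still has 0 df. Stacking visits does not make the listed model work either.

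**The case against.** The best defence is that the sentence is loose rather than wrong. It never says fixed, and it lists the baseline score among the factors although the sentence before calls it a covariable. Subject may therefore only name the unit of analysis, which fits the emphasis on subjectwise scores. On that reading, or with subject random, the analysis is ordinary ANCOVA. The fixed-factor failure also reveals itself: with no error df there is no p-value, so the literal model cannot yield a wrong published test. This much stands: the intended model is fairly clear, the analyst has little latitude, and the slip is probably one of wording. But the plan nowhere gives subject that meaning, and under the lenient reading the term is redundant, so deletion is right either way.

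Other points carry less weight:

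- *Treatment has 2 df if entered first.* True for sequential df. Error df are still 0, so nothing can be tested.
- *A repeated-measures model may have been meant.* The section has no visit term, treatment-by-visit term or covariance structure, and it defines the intent-to-treat set separately at each time point. That other time points are analysed one by one is an inference, but the likelier one.
- *Section VII allows household members to receive the same product, so subjects are not all independently assigned.* The 296 and 297 residual df do assume independent subjects. That is a separate question and does not help the subject term, which does not represent households.

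**Conclusion.** The concern holds: the primary model is wrong as written. Entered as a fixed factor, subject leaves 0 residual df at any N with one row per subject, and treatment has 0 df beyond it. The Tukey comparisons and the baseline comparison cannot be computed. Deleting the term restores 2 treatment df and 296 residual df at month 6, and 297 residual df at baseline, with 300 completers.

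The conclusion rests on one score per subject in each analysis, one treatment per subject, and subject being fixed. If it is random, the term is harmless but useless. The practical harm is limited, since the rest of the section points to treatment plus baseline. It should still be fixed, because no other sentence specifies the primary model.

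**What to change.** In Efficacy Analysis, delete subject from the list of model terms and state the model as: month 6 Index score = treatment + baseline Index score, with Tukey-adjusted pairwise comparisons of the adjusted means. State the baseline comparison as a one-way ANOVA on treatment. Say that the same wording applies to the intent-to-treat set, the other time points and the site subsets.

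If the sponsor did intend a repeated-measures analysis across visits, it has to be written out as such, with visit and treatment-by-visit terms and a covariance structure.

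Whether to adjust for stratification factors is a separate matter. It first needs sections VI (smoking and tobacco use) and VII (baseline plaque and gingival scores, and age) reconciled.

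The cost is two sentences of analysis wording. Data collection, visits and enrolment do not change.

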#### STUDY OBJECTIVES

The objectives of this 6-month clinical research study are:

- 1) Primary objective is to evaluate the safety and efficacy of two baking soda dentifrices, containing 20% and 35% baking soda, (test products) compared to that of a non-baking soda dentifrice (negative control) in reducing gingival inflammation and bleeding.
- 2) Secondary objective is to evaluate the efficacy of two baking soda dentifrices compared to that of a non-baking soda dentifrice in reducing plaque.

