#### VII. SUBJECT ASSIGNMENT TO TREATMENT GROUPS

At the baseline visit, following the clinical assessments, the study population will be evenly distributed into three treatment groups of approximately equal size and equivalence. Qualified subjects will be randomly assigned to the three treatment groups based on a randomization scheme developed using the baseline plaque and gingival assessment scores and age for stratification. The study staff responsible for random assignments will be blinded to the product treatments. Allowance will be made for members of the same household co-habiting at one address to receive the same products to prevent inadvertent switch-over.

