#### Sample Size

The planned sample size for this study is to complete with at least 100 evaluable subjects per treatment group (300 total subjects). Approximately 320 subjects will be enrolled, to assure that at least 100 evaluable subjects per group complete the study. Based on a 3-month pilot clinical study, in which the coefficient of variation for the plaque index (PI) was 18.1%, the coefficient of variation for the gingival index (MGI) was 7.2%, and the coefficient of variation for the bleeding index (GBI) was 61.3%, 100 subjects per group will give a power of over 95% for detecting a 20% difference between groups.

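### Tukey's all-pairs adjustment is valid but less efficient than a control-only method for the two comparisons in the objectives; on GBI it costs up to about 5 points of power

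*Combined protocol and SAP*

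**What the plan says.** The primary objective sets the two baking soda dentifrices against one comparator: "test products) compared to that of a non-baking soda dentifrice (negative control) in reducing gingival inflammation and bleeding". The secondary objective asks the same of plaque. The closing paragraph of the Introduction also describes two baking soda products compared with a non-baking soda product. None of these places asks whether 35% differs from 20%.

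The Efficacy Analysis section makes the month 6 index scores the primary endpoints and fits an ANCOVA with the baseline score as covariate. It then states: "Post-ANCOVA pairwise treatment comparisons of the adjusted means will be performed using t-tests utilizing Tukey's adjustment for multiple comparisons". On the error rate it says: "All statistical tests of hypotheses will be two-sided, and employ a level of significance of" 0.05. With three groups, this family has three pairs, including 20% versus 35%.

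The Sample Size section reports three pilot CVs: 18.1% for PI, 7.2% for MGI and 61.3% for GBI. Its conclusion, drawn once for all three indices, is that "100 subjects per group will give a power of over 95% for detecting a 20% difference between groups". It mentions no multiplicity adjustment in that statement.

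**The concern.** Tukey's critical value is set so that the largest of three pairwise differences is controlled. If only two differences answer the trial's question, and both share the control arm, a smaller critical value gives the same familywise protection over those two. Under the present text the third pair is paid for by the two that the objectives name.

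This matters only where power is short. Bleeding is part of the primary objective and the month 6 index scores are the primary endpoints, so GBI is a primary index. Its pilot CV is more than three times that of PI and more than eight times that of MGI. At stake is some avoidable loss of power on GBI, together with a mismatch between the objectives and the family of tests.

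**Working it through.** **Inputs from the plan.** 100 evaluable subjects per group; a 20% difference; CVs of 18.1% (PI), 7.2% (MGI) and 61.3% (GBI); two-sided 0.05; "three treatment groups of approximately equal size and equivalence", taken as 1:1:1.

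**Assumptions.** The CV is the SD used in the analysis, as a share of the mean, and is equal across arms. Error degrees of freedom are 300 − 3 = 297; removing one for the covariate changes nothing visible.

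**Step 1: the plan's own power figure, unadjusted.** Noncentrality = 0.20 / (CV × √(2/100)), with critical t 1.968.
- PI: 0.20 / (0.181 × 0.1414) = 7.81, power about 100%.
- MGI: 0.20 / (0.072 × 0.1414) = 19.64, power about 100%.
- GBI: 0.20 / (0.613 × 0.1414) = 2.307, power 63.3%.

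The stated figure of over 95% is reproduced for PI and MGI but not for GBI.

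**Step 2: critical values for the comparisons with control.**
- Tukey, three groups: 3.331 / √2 = 2.356.
- Dunnett, two-sided, two contrasts with correlation 0.5: 2.223 (numerical integration).
- Ratio: 2.223 / 2.356 = 0.944, so simultaneous intervals are about 5.6% narrower with Dunnett.

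**Step 3: GBI power per control comparison** (noncentral t, 297 df, noncentrality 2.307).
- Tukey: 48.2%.
- Dunnett: 53.4%.
- Gain: 5.3 points before rounding.

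PI and MGI stay at about 100% under either method.

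**Step 4: allowing for the baseline covariate.** The plan gives no correlation r between baseline and month 6, so r is an assumed range. Noncentrality becomes 2.307 / √(1 − r²).

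| Assumed r | Tukey | Dunnett | Gain (points) |
|---|---|---|---|
| 0.3 | 52.6% | 57.8% | 5.2 |
| 0.5 | 62.1% | 67.1% | 4.9 |
| 0.6 | 70.1% | 74.6% | 4.4 |
| 0.7 | 80.9% | 84.3% | 3.4 |
| 0.8 | 93.1% | 94.7% | 1.6 |

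Gains are taken before rounding.

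**Step 5: larger effects, with r = 0.** At a 30% difference power is about 86% (Tukey) and 89% (Dunnett). At 35% it is 95.3% and 96.5%, and at 40% it is 98.8% and 99.1%.

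**Step 6: the gain expressed as sample size.** The ratio is ((2.356 + z) / (2.223 + z))². With z = 0.842 (80% power) it is 1.09, and with z = 1.645 (95% power) it is 1.07.

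**Step 7: step-down Dunnett.** The larger statistic is compared with 2.223 and, if that succeeds, the other with 1.968. In simulation, with both test products 20% better than control on GBI, power per comparison is about 58%. If only one product works, the step-down version adds almost nothing to single-step Dunnett.

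**The case against.** The strongest reply is that nothing here is wrong. Tukey is prespecified and valid, and it matches the family that the Efficacy Analysis section declares, since that section plans pairwise comparisons in general. A sponsor with two strengths in the trial may want 20% versus 35% protected. That stands. It means the mismatch can be resolved from either side, by narrowing the family or by widening the objectives.

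A second reply is that Dunnett is not the only way to recover power. With exactly three groups, an overall F-test followed by unadjusted pairwise t-tests also controls the familywise rate for all three pairs. In simulation it gives about 56% on GBI when both products are 20% better or only one is, and about 51% for a fully effective product when the other has half the effect. That also stands: single-step Dunnett is one reasonable choice among several.

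A reader might also infer four stronger things that the documents do not support.
- *The error rate is inflated.* It is not; within an index, Tukey covers these two comparisons and one more.
- *The mismatch costs 15 points.* That is the gap between Tukey and no adjustment (63.3 − 48.2 = 15.1). Two comparisons with a control still call for some adjustment, so the relevant gap is the one to Dunnett.
- *Dunnett repairs the power statement.* It does not. With the CV at face value, GBI power is about 63% before any adjustment and 53% with Dunnett.
- *The change is free.* It is not; a comparison now in the protected family loses unconditional protection.

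**Conclusion.** The point holds as one of efficiency and alignment. The objectives ask for two control comparisons and the analysis protects three pairs. On GBI this costs about 5 points of power per control comparison (48% against 53%) at 100 per group, a 20% difference and an analysis SD of 61.3% of the mean.

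The size depends on those conditions. The loss stays above 4 points up to an assumed baseline correlation of 0.6, falls to 1.6 points at 0.8, and shrinks as the true effect grows. For MGI, the other index in the primary objective, and for PI, it is about nil. The documents do not say whether the 61.3% is already adjusted for baseline.

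The Sample Size statement is a separate and larger matter. At face value it fails for GBI even without adjustment. A baseline correlation near 0.8 would bring the unadjusted figure to about 97%, but the plan states no correlation and claims no such gain.

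**What to change.** Before unblinding, amend the multiplicity sentence in the Efficacy Analysis section along these lines:

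- Compare each test dentifrice with the negative control on the ANCOVA-adjusted means, using Dunnett's adjustment (or step-down Dunnett) at two-sided 0.05.
- Test 20% versus 35% at 0.05 only if both control comparisons are significant. Otherwise report that difference as an estimate with a 95% interval and make no claim from it.

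This keeps familywise control over all three pairs within an index. If either control hypothesis is true, the third test is reached only after an error has already been counted. If neither is true, the third test is the only one that can err, and it is run at 0.05.

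If the sponsor wants 20% versus 35% fully protected, add it to the Study Objectives and keep an all-pairs method.

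Either route takes a line or two of text, with no added subjects or visits. The cost of the first is that 20% versus 35% loses unconditional protection. The step-down version also lacks simple matching simultaneous intervals, so single-step Dunnett is preferable if intervals are to be reported. The power statement for GBI needs its own correction whichever route is taken.
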